### 7.2.4 Reporting of (Serious) Adverse Events and other safety related events

All SAEs/SADEs and DDs that could have led to a serious adverse device effect must be reported, whether or not considered causally related to the medical device, or to the study procedure(s). All the above-mentioned events will be recorded in the eCRF no later than 24 hours after acknowledging the occurrence of the event. If the eCRF system is not available, the paper SAE/DD/Device Incidents reporting form will be filled in (in English language, written in clear capital letters) and must be sent via email to the Sponsor at the email address indicated below.

Day 0 is the day the Investigator becomes aware of an event occurred to the subject, and it is used by the Sponsor as reference day for regulatory purposes. Each SAE and SADE must be tracked and assessed by the Sponsor. The Sponsor will report any SAEs/SADEs to the relevant Independent Ethics Committee (IEC) as required by local requirements of the committee and to the Competent Authority. The Sponsor will determine whether a SADE is considered “anticipated” or not. Each DD must be tracked and assessed by the Sponsor. Any DD that might have led to a SAE if suitable action had not been taken or intervention had not been made or if circumstances had been less fortunate will be reported to the Competent Authority.

All SAE/DD/Device Incidents, independently of their causal relationship, must be reported immediately (within 24 hours) in the eCRF SAE form; if the eCRF system is not available, the paper reporting form must be reported immediately (within 24 hours from awareness) via email or Certified Electronic Mail by the Investigator or his delegated to:

[name], Endostart s.r.l., [name].

[contact]

Certified Electronic Mail: [[contact]](mailto:[contact])

Email: [[contact]](mailto:[contact]) and [[contact]](mailto:[contact])

Initial notification should include:

- Identification of the Principal Investigator: name, address, study center, telephone number;
- Study protocol number;
- Subject's identification (ID number in the study, date of birth, sex, relevant medical history);
- Device name or code, beginning and end of treatment;
- Description of event and its onset;
- Measures undertaken to treat it;
- Opinion of the Investigator about the relation of the event to the tested medical device.

Subjects experiencing SAEs must be monitored until resolution, and acceptable stabilization in the event of chronicity.

In the event of a death, the pathology report will be always requested.

In case of malfunctioning of the medical device, the Investigator will immediately inform the Sponsor by using the same phone and email addresses specified above. The defected medical device will be shipped to the Sponsor, in order to allow all necessary assessments.

In case of malfunctioning of the study medical device, the patient must not be penalized. In order to allow the treatment completion, a set of rescue medical device will be forwarded to each physician.

Once per year for the duration of the research or on request, the Sponsor transmits a safety report with all the available safety information to the Competent Authority (CA) and to the sites involved. This report includes notably the list of all the suspected serious adverse reactions and an analysis of the information regarding the safety of individuals participating in the research.

The Investigator will submit, on request, copies of all reportable SAE reports to the Ethics Committee concerned. Once per year for the duration of the research or on request, the Investigator or its delegated transmits the safety report with all the available safety information to the local Ethic Committee.

### 7.3 Follow up of (Serious) Adverse Events

Follow-up of SAEs/SADEs/device incidents

- Reporting of SAEs/SADEs/device incidences from the investigational site begins from signing of informed consent and ends at the last study visit/last follow-up contact.
- All new SAEs/SADEs/device incidences occurring beyond this time frame and coming to the attention of the investigator must be recorded only if they are considered (in the opinion of the Investigator) causally-related to the investigational product. Thus, only SAEs/SADEs/device incidences related to the investigational product will be followed after the Visit 2, until resolution, stabilization or patient loss at follow-up.
- Reports of SAEs/SADEs/device incidences occurred during the study or after the site closure should be reported directly from the Investigator to the Sponsor Safety Contact see Section 7.3.4.
- All SAEs/SADEs/device incidences should be followed-up in order to elucidate as completely and practical as possible their nature and/or causality. The follow-up

information should be submitted until resolution of all queries, clinical recovery is complete, laboratory results have returned to normal, until progression has been stabilized or until the patient is lost to follow-up. Follow-up may therefore continue after the patient has left the study.

- In case of death, a comprehensive narrative report of the case should be prepared by the Investigator and sent to the Sponsor Safety Contact by email together with the SAE form, retaining a copy on site filing it in the patient folder.
- If an autopsy is performed, copy of the autopsy report should be actively sought by the Investigator and sent to the Sponsor Safety Contact as soon as available, retaining a copy on site and filing it in the patient folder.

## 8. STATISTICAL METHODS

### 8.1 Hypothesis

This study is designed to test the null hypothesis that the proportion of 'event' (intended as procedure incomplete or serious adverse event) is equal or greater than 20%. The alternative hypothesis is that the proportion of 'event' is less than 20%. In statistical terms:

$$H0: p \geq 20\%$$

$$H1: p < 20\%$$

Where:

$p$  = true proportion of patients with event

### 8.2 Determination of Sample Size

Efficacy (first primary objective) will be assessed by measuring the colonoscopy completion rate in long-lasting procedures, which is a measurable parameter of clinical value recognized by international medical societies. Safety (second primary objective) will be assessed by measuring the rare of adverse events. They are classified into: serious gastrointestinal events; myocardial infarction; stroke; pneumonia. Based on the literature [30]; their occurrence rates in screening or surveillance colonoscopy are 47 persons, 4 persons, 7 persons and 10 persons per 100'000, respectively.

These two objectives are merged in one indicator, which is equal to 1 for each subject if the procedure is incomplete or an adverse event occurs, and 0 otherwise.

The non-completion rate of long-lasting colonoscopies conducted with Endorail is expected to be around 10%. This will be compared to the above-mentioned threshold of 20% for incomplete procedures. It should be noted that this threshold is conservative and represents the most critical setting for comparison with respect to the state of the art, as it is derived from the lower bound of the range from the literature.

When including the safety to provide the expected value of the indicator for Endorail and the corresponding threshold, the above values of 10% minimally change, as the adverse event

occurrence rate is 0.068% (given by the sum of the occurrence of the 4 events reported above per 100'000 persons, expressed in percentage).

With a significance level  $\alpha$  of 5%, assuming a proportion of outcome of 10.1%, 85 patients allow to test with a power of 80% the  $H_0: p \geq 20\%$  vs  $H_1: p < 20\%$ , where 20% is the estimated percentage of incomplete procedure from literature.

The chosen number is then increased by the 10% to account for possible drop-out (e.g., cases to be discarded, losses to follow-up, etc.), resulting in  $85/0.90 = 95$  patients to be actually enrolled.

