#### 1.2.3 Long lasting colonoscopy

A colonoscopy can be defined as difficult or long-lasting when caecal intubation time is longer than 10 minutes. Long lasting colonoscopies are cause of stress and delays in the workflow. Moreover, longer procedures are characterized by more traumatic manoeuvres, increased pain and discomfort, higher sedation requirements and higher risk of severe complications such as cardiorespiratory events and bowel perforation.

As data from literature shows that about 80% of all diagnostic colonoscopies are typically completed in less than 10 minutes, the long-lasting colonoscopy subset represents approx. 20% of the total procedures. Indeed, since nearly virtually all incomplete colonoscopies are also long-lasting, the risk of incompleteness in this subset of patients increases nearly five-fold (i.e., for a 5x increase, the lower bound of the rate increases from 4% to 20%) [1][7][17][20].

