### 7.1 Medical Device – Class I

#### 7.1.1 Definition of (Serious) Adverse Events and other safety related events

An Adverse Event (AE) is defined as “any untoward medical occurrence, unintended disease or injury, or untoward clinical sign (including abnormal laboratory findings) in subjects, users or other persons, whether related to the investigational medical device”.

This definition is restricted to events related to the investigational medical device and includes: events related to the investigational medical device, events related to the study procedures and events related to the device users or to other persons involved.

An **Adverse Device Effect (ADE)** is defined as an AE related to the use of the medical device.

This definition includes any AEs resulting from insufficiencies or inadequacies in the instructions for use, in the deployment, the implantation, the installation, the operation, or any malfunction of the medical device. It also includes any AE resulting from a user error or from the intentional abnormal use (misuse) of the investigational medical device. All ADEs will be classified as Serious/Non-Serious according to the categories of seriousness and as Mild, Moderate or Severe according to the intensity classification. In addition, the investigator will always be asked to express his/her judgment about the causality relationship with the medical device.

**Device deficiencies (DDs)** are defined as any inadequacy of the medical device with respect to its identity, quality, durability, reliability, safety or performance, including malfunctions, use errors, and inadequate labelling. A malfunction is defined as a failure of the investigational medical device performance compared to its intended purpose, when used in accordance with the instructions for use or protocol. All DDs will be documented during the clinical investigation and reported to the Sponsor on the appropriate form.

A device deficiency not leading to an AE but that could be the cause of a medical occurrence if suitable actions have not been taken, if intervention had not been made, or if circumstances had been less fortunate, must be reported in the same way of an adverse event.

A **Serious Adverse Event (SAE)** is any untoward medical occurrence or effect that:

- Results in death;
- Is life-threatening;

- Requires inpatient hospitalisation or prolongation of existing hospitalisation;
- Results in persistent or significant disability or incapacity;

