- Is a congenital anomaly or birth defect;
- Is an important medical event (i.e. important medical reactions that jeopardize the patient or may require intervention to prevent one of the other outcomes listed in the above definition).

The term “life-threatening” in the definition refers to an event in which the subject was at risk of death at the time of the event; on the contrary, it does not refer to an event which hypothetically might have caused death if it was more severe.

In addition, important medical events that may not be immediately life-threatening or result in death, or require hospitalisation, but that may jeopardise the patient or may require a medical intervention to prevent one of the other outcomes listed above, should also be considered serious. (ICH E2A).

SAEs should be followed up until resolution or stabilisation. Participants with ongoing SAEs at the moment of their study termination (including safety visit) will be further followed up until recovery or until stabilisation after the study termination.

Any adverse event which does not fall into the above-described categories is to be defined as Non-Serious.

Seriousness must not be confused with the intensity of the event (severity).

Planned hospitalization for a pre-existing condition, or a procedure required by protocol, without serious deterioration in health, is not considered a SAE, but part of the medical history.

Causal Relationship of SAE [MEDDEV 2.7/3 revision 3, May 2015]:

A causal relationship towards the medical device or study procedure should be rated as follows:

- **Not related:** The relationship to the device or procedures can be excluded.
- **Unlikely:** The relationship with the use of the device seems not relevant and/or the event can be reasonably explained by another cause, but additional information may be obtained.
- **Possible:** The relationship with the use of the investigational device is weak but cannot be ruled out completely. Alternative causes are also possible.
- **Probable:** The relationship with the use of the investigational device seems relevant and/or the event cannot reasonably be explained by another cause.
- **Causal relationship:** The serious event is associated with the investigational device or with procedures beyond reasonable doubt.

Device deficiencies that might have led to an SAE are always related to the medical device.

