#### **8.4.2 Interim analyses**

Two interim analyses will be planned, a first when 40% of the sample size (38 patients) is reached and a second when 60% of the sample size (57 patients) is reached. During these interim analyses the significance will be tested. If significance is found, the trial can be terminated with the patients already collected.

38 patients guarantee a statistical power of 80% if at least 93.9% of these are free of 'event' (intended as procedure incomplete or serious adverse event). 57 patients guarantee a statistical power of 80% if at least 91.8% of these are free of 'event'.

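### Section 8 defines the primary event inconsistently and does not tie the no-device-related-SAE criterion to the test or early stopping, and 95 patients cannot show that SAEs are not increased

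*Combined protocol and SAP*

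**What the plan says.** **Event definition.** Section 8.1 states the null hypothesis for the proportion of patients with an event, "intended as procedure incomplete or serious adverse event) is equal or greater than 20" percent. Section 8.4.2 repeats that definition for the interim looks: "intended as procedure incomplete or serious adverse event). 57 patients guarantee a statistical power of 80" percent. Section 8.2, which builds the variable actually tested, says that the two objectives are "merged in one indicator, which is equal to 1 for each subject if the procedure is incomplete or an adverse event occurs". Just before this, it says of adverse events: "They are classified into: serious gastrointestinal events; myocardial infarction; stroke; pneumonia". For planning, it states that the "occurrence rate is 0.068% (given by the sum of the occurrence of the 4 events reported above per 100'000 persons".

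Section 7.1.1 defines an SAE more broadly than those four categories. Its criteria include "Requires inpatient hospitalisation or prolongation of existing hospitalisation" and "Is an important medical event (i.e. important medical reactions that jeopardize the patient". It also says both that an adverse event need not be related to the device and that the definition is limited to device-related events.

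**Success and stopping.** Sections 2.1 and 3.1 join efficacy AND safety, and 3.1 makes the absence of device-related SAEs a primary endpoint. Sections 4.6, 8.3 and 8.4.2 allow the trial to end at 38 or 57 patients if the indicator is significant. Section 8.4 specifies one test, a one-tailed exact binomial test of the indicator.

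**Safety comparison.** Section 2.1 sets out to show that SAEs are not increased by the device, and explains this chiefly as the absence of device-related SAEs. Section 3.1 adds that adverse event rates are to be equal to or lower than without the device. Section 8.4 plans only descriptive adverse event tables.

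**The concern.** The trial has one confirmatory test, and the same patient can be a failure under one sentence and a success under another. A serious cardiorespiratory event that is not a myocardial infarction, stroke or pneumonia is an event under 8.1 but is not on the 8.2 list. Section 1.2.3 says that longer procedures carry a "higher risk of severe complications such as cardiorespiratory events and bowel perforation", so such cases are foreseeable here. Section 8.4 leaves detail to an analysis plan finalised before database lock. That may come after the looks at 38 and 57 patients in an open-label trial.

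H0 can also be rejected, and the trial ended early, with a device-related SAE among the tolerated events. Section 8 does not say that the joint primary criterion is then missed. The 20% limit comes from incompletion, so rejecting H0 is not in itself evidence of safety.

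Finally, zero SAEs could be reported as showing no increase when the data could not exclude a rate of several percent.

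**Working it through.** **Inputs.** From 8.1, 8.2 and 8.4: p0 = 20%, one-sided 5%, exact binomial test, expected incompletion about 10%, planning value 10.1%, 85 evaluable and 95 enrolled. From 8.3 and 8.4.2: looks at 38 and 57. The documents give no SAE rate beyond 0.068% and no any-AE rate, so all other rates below are assumptions.

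**1. The plan's own figures.**
- (47 + 4 + 7 + 10)/100,000 = 0.068%.
- Normal approximation: n = [(1.645·√(0.2·0.8) + 0.842·√(0.101·0.899))/(0.2 − 0.101)]² = 84.8, so 85; 85/0.90 = 94.4, so 95.
- Under the exact test of 8.4, power at 10.1% is 76% at 85 and 84% at 95. These are the baselines used below.

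**2. How many events the test tolerates.** The largest c with P(X ≤ c | n, 0.20) ≤ 0.05 is:

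| n | c | P(X ≤ c) | P(X ≤ c+1) |
|---|---|---|---|
| 38 | 3 | 0.0387 | 0.0986 |
| 57 | 6 | 0.0451 | 0.0934 |
| 85 | 10 | 0.0332 | 0.0627 |
| 95 | 12 | 0.0424 | 0.0747 |

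**3. Effect of the definition on power.** With 10% incompletion and an independent event rate q, p = 1 − 0.9(1 − q). The 10.1% planning value leaves room for q = 1 − 0.899/0.9 = 0.11%.

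| Reading | q | Power, n=95 | Power, n=85 |
|---|---|---|---|
| Planning value, p = 10.1% | 0.11% | 84% | 76% |
| Any SAE (assumed) | 0.2% | 83% | 75% |
| Any SAE (assumed) | 0.5% | 81% | 73% |
| Any AE, literal 8.2 (assumed) | 2% | 67% | 58% |

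**4. The missing safety condition.** Let q be the device-related SAE rate, with 10% incompletion. The single-look columns are P(X ≤ 12 | 95, p) and (1 − q)^95 · P(X ≤ 12 | 95, 0.10). For example, at q = 0.068% the second is 0.937 × 0.848 = 0.795. The last column follows the event count and whether any SAE has occurred through looks at 38, 57 and 95, each at an unadjusted 5%, stopping at the first significant look.

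| q | Reject H0, single look at 95 | Reject with no device-related SAE, single look at 95 | Reject with at least one, three looks |
|---|---|---|---|
| 0.068% | 0.843 | 0.795 | 2.8% |
| 0.2% | 0.833 | 0.701 | 7.8% |
| 0.5% | 0.809 | 0.527 | 17.5% |
| 1% | 0.767 | 0.326 | 29.2% |

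The 0.068% row treats every SAE at that rate as device-related. The 1% row is about 15 times the documented rate (0.01/0.00068 = 14.7).

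**5. What zero SAEs would show.** The expected number in 95 patients is 95 × 0.00068 = 0.065. With none observed, the one-sided 95% upper limit is 1 − 0.05^(1/n): 3.1% at 95, 5.1% at 57 and 7.6% at 38. The first is about 46 times 0.068%.

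**The case against.** Five objections deserve an answer.

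- **Section 8.2 is loosely worded and 8.1 governs.** This is largely right about non-serious events. Section 8.2 lists serious categories just before the indicator, and its 0.068% fits only rare, serious events. A reader might infer that petechiae and abdominal pain were meant to count and that the trial is badly underpowered. The documents do not support that inference, and the any-AE power figure rests on an assumed rate. What stands is that 8.2 is where the indicator is built, no sentence says which section prevails, and any SAE is not the same as the four categories.
- **Section 3.1 already requires zero device-related SAEs.** That is so. Such an event fails 3.1 whether or not Section 8 repeats it, it counts as one event under the SAE wording, and early stopping is optional. A reader might infer that Section 8 contradicts 3.1. It does not; a link is missing. The sponsor's discretionary benefit/risk ground in 4.6 does not supply it, because it does not define success.
- **The rejection figures are not the chance of missing 3.1 as a whole.** Correct: they cover the SAE limb only. At 10% true incompletion and no SAE, P(X ≤ 12) − P(X ≤ 9) = 0.848 − 0.518 = 0.33 at n=95. So an observed rate above 10% would accompany rejection about a third of the time for that reason alone. That is a separate point.
- **The higher rates are assumed.** Also correct. At the only documented rate the three-look figure is 2.8%, and it presumes that every SAE is device-related.
- **The safety objective is explained as absence of device-related SAEs, which can be observed.** This stands. A reader might infer that no safety criterion here can be assessed, which goes too far. The claim of no increase, and the equality or reduction in 3.1, remain out of reach.

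**Conclusion.** The point holds in three parts of unequal weight.

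**Definition.** The event in the only confirmatory test is inconsistently defined. The practical choice is any SAE versus the four categories. It costs about 1 to 3 points of power at assumed all-SAE rates of 0.2% to 0.5%. The main reason to settle it is that patients must be classified the same way at every look.

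**Missing link.** Neither the test nor early stopping carries the 3.1 criterion of no device-related SAE. The chance of rejection with such an event is 2.8% at the documented rate and up to 29.2% at an assumed 1%. The low end is the reference case. These figures assume 10% incompletion, independence of SAEs and incompletion, and stopping at the first significant look.

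**Precision.** No increase in SAEs, and equality or reduction of adverse event rates, cannot be shown with 95 patients. The 0.068% reference comes from screening or surveillance colonoscopy. This trial excludes screening, and 1.2.3 gives longer procedures a higher risk, so the match is only partial. A higher true reference would not rescue the claim, because the limit of 3.1% depends on the sample size alone.

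**What to change.** Before the first interim look:

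1. Use one event definition in 8.1, 8.2 and 8.4.2: incomplete procedure or any SAE, regardless of relation to the device. Make 7.1.1 consistent with this by removing the sentence that limits adverse events to device-related ones. Say that the four categories in 8.2 are only the source of the planning rate, so 0.068% may understate the all-SAE rate.
2. State in 4.6, 8.3, 8.4 and 8.4.2 that a claim of overall success, interim or final, needs both rejection of H0 and the 3.1 criterion of no device-related SAE. Name the causality grades of 7.1.1 that count as device-related.
3. Report incompletion and SAE proportions separately, each with exact 95% limits.
4. In the synopsis, 2.1 and 3.1, replace the claims of no increase and of equality or reduction with descriptive wording that states the precision above.

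**Cost.** The changes are to wording, with a more modest safety claim. Counting all SAEs leaves power of 81% at 95 at an assumed rate of 0.5%, but 73% if only the 85 evaluable patients are reached. Making the SAE criterion binding lowers the chance of rejection with no device-related SAE (single look at 95) from 84% to 79% at 0.068%. At assumed device-related rates of 0.2%, 0.5% and 1%, that chance is 70%, 53% and 33%. Section 3.1 already implies this cost. None of these figures includes the 10% incompletion criterion of 3.1.

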#### **4.7 Replacements**

Patients who withdraw the informed consent before the completion of the procedure can be replaced by newly recruited patients. Similarly, for patients who are found to be lost to follow-up following the procedure completion and therefore cannot be reached by phone for the scheduled follow-up visit (Visit 2) a second and third attempt should be made after the second and third week; if the patient is still untraceable it can also be replaced by newly recruited patients (See section 5.5).

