### **8.3 Statistical criteria of termination of trial**

Interim analyses will be considered, to be able to terminate the study in advance if significance is found. In particular, when 38 patients (40% of the sample size) and 57 patients (60% of the sample size) are reached, the significance will be tested. If significance is found, the trial can be terminated with the patients already collected.

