### **8.4 Planned Analyses**

The statistical analysis plan will be finalized before Data Base Lock and it will include a more technical and detailed description of the statistical analyses described in this section. This section is a summary of the planned statistical analyses.

All data obtained in this study and documented in the eCRFs will be listed and summarized as appropriate:

- for quantitative variables: standard quantitative statistics (N, mean, standard deviation, median, interquartile range, minimum and maximum);
- for qualitative variables: frequency distribution [number of non-missing observations (N) and percentages (%)].

A statistical test will be performed to assess the significant difference of the indicator with respect to the threshold and statistically prove efficacy of Endorail in long-lasting procedures. Due to the type of variable, the exact binomial test will be adopted. Additionally, considering as alternative hypothesis that the rate observed in the analyzed population is less than the respective threshold, the one-tailed test will be adopted.

Medical adverse events and medical device adverse events will be collected during the study.

The number of adverse events (AEs) – related or not to the medical device – and the number and proportion of patients with at least one AE will be presented.

All adverse events will be tabulated by System Organ Class (SOC) and Preferred Term (PT) after medical coding using the Medical Dictionary for Regulatory Activities (MedDRA) thesaurus version 24.1. The primary SOC and the PT will be used for the analysis of the frequency

distribution.

The frequency of occurrence of specific adverse events (gastrointestinal bleedings, intestinal perforation, mucosal petechiae, abdominal pain) will be presented by means of default descriptive statistics.

Statistical analyses will be carried out using R Statistical Software (Foundation for Statistical Computing, Vienna, Austria).

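### The stated 80% power at 85 patients does not hold for the planned exact binomial test, which gives about 76% at a single look

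*Combined protocol and SAP*

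**What the plan says.** The synopsis and section 8.2 (Determination of Sample Size) give the same calculation. The hypotheses are H0: p ≥ 20% against H1: p < 20%, where p is the proportion with an incomplete procedure or an adverse event. At a 5% significance level, "assuming a proportion of outcome of 10.1%, 85 patients allow to test with a power of 80" per cent. Section 8.2 continues: "The chosen number is then increased by the 10% to account for possible drop-out", and computes 85/0.90 = 95 patients to enrol. So 85 is the number expected to remain for analysis. No sample-size formula or software routine is named.

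Section 8.4 (Planned Analyses) chooses the test: "Due to the type of variable, the exact binomial test will be adopted", and makes it one-tailed.

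Section 8.3 adds two early looks: "when 38 patients (40% of the sample size) and 57 patients (60% of the sample size) are reached, the significance will be tested". Section 8.4.2 attaches power statements to them: "38 patients guarantee a statistical power of 80% if at least 93.9% of these are free of" event, and "57 patients guarantee a statistical power of 80% if at least 91.8% of these are free of" event.

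**The concern.** The sample size is justified by a power figure, and a power figure belongs to a particular test. An exact binomial test is discrete: at a given n its rejection limit is a whole number of events, and its actual type I error can be well below the nominal 5%. When that happens, power falls below what a continuous approximation predicts. If the 80% came from such an approximation, the planned test would not deliver it at 85 patients.

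The stated power is the only quantitative justification given for the size of a single-arm trial with one primary hypothesis test. If it is wrong, the type II error is larger than the sponsor and the ethics committees were told, and anyone who recomputes it with the plan's own test will get a different answer.

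**Working it through.** **Inputs.** Null rate 20% (sections 8.1 and 8.2); assumed true rate 10.1%, level 5% and evaluable n = 85 (section 8.2); one-tailed exact binomial test (section 8.4); 95 enrolled (section 8.2).

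**1. Reproducing the plan's figure.** One-sample, one-sided normal approximation without continuity correction:

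n = [(z₀.₉₅·√(p₀(1−p₀)) + z₀.₈₀·√(p₁(1−p₁))) / (p₀−p₁)]²

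= [(1.645·√(0.2·0.8) + 0.842·√(0.101·0.899)) / 0.099]²

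= [(0.658 + 0.254) / 0.099]² = 84.8, rounded up to 85.

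Power of this approximation at n = 85 is 80.1%. Other common variants do not give 85: two-sided 110, continuity-corrected 95, arcsine 79, unpooled (Wald) variance 58, null variance 101. That this is the formula used is an inference.

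**2. The planned exact test at n = 85.** The rejection limit c is the largest whole number with P(X ≤ c | 85, 0.20) ≤ 0.05.

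- P(X ≤ 10 | 85, 0.20) = 0.0332, so 10 events reject.
- P(X ≤ 11 | 85, 0.20) = 0.0627, so 11 events do not.
- Hence c = 10, and power is P(X ≤ 10 | 85, 0.101) = 0.763.

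The shortfall is 80 − 76.3 = 3.7 points, and the type II error is 23.7% rather than 20%. Rounding of the assumed rate does not explain it: at exactly 10.0% the power is 77.2%.

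**3. Neighbouring sample sizes (exact, single look, true rate 10.1%).**

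| n | Reject at ≤ | Size | Power |
|---|---|---|---|
| 82 | 10 | 4.6% | 79.7% |
| 84 | 10 | 3.7% | 77.4% |
| 85 | 10 | 3.3% | 76.3% |
| 87 | 10 | 2.7% | 73.9% |
| 88 | 11 | 4.6% | 82.5% |
| 90 | 11 | 3.8% | 80.5% |
| 93 | 11 | 2.7% | 77.3% |
| 94 | 12 | 4.7% | 84.8% |
| 95 | 12 | 4.2% | 84.0% |

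No n up to 87 reaches 80%; the best is 79.7% at 82. Power is above 80% at 88–90, below it at 91–93, and above it from 94 on (checked to n = 160).

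**4. Effect of drop-out.** As an illustration, assume patients are lost at random from 95 and not replaced. With 10% loss the evaluable n follows Bin(95, 0.90). The probability of landing where power is below 80% is P(n ≤ 84) + P(85–87) + P(91–93) = 0.351 + 0.394 + 0.033 = 0.778, and average power is 77.2%. With 5% loss the probability is 0.539 and average power is 79.6%.

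**5. The section 8.4.2 figures.** Taking the printed rates as true rates, the exact test gives P(X ≤ 3 | 38, 0.061) = 80.0% and P(X ≤ 6 | 57, 0.082) = 81.6%. Both statements hold. The event-free rate needed for 80% power is 93.93% (approximation) or 93.90% (exact) at 38, so that figure cannot tell the two methods apart. At 57 it is 91.78% or 91.60%, and the printed 91.8% fits the approximation. Only the figure for 85 fails.

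**6. Adding the looks at 38 and 57.**

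| Event limits at 38 / 57 / final N | Type I error | Power at 10.1% |
|---|---|---|
| Unadjusted 3 / 6 / 10, N = 85 | 7.6% | 81.3% |
| Unadjusted 3 / 6 / 12, N = 95 | 8.4% | 86.9% |
| O'Brien-Fleming-type 1 / 4 / 10, N = 85 | 3.6% | 76.7% |
| Pocock-type 2 / 5 / 10, N = 85 | 4.6% | 78.1% |
| O'Brien-Fleming-type 0 / 4 / 12, N = 95 | 4.4% | 84.2% |
| Pocock-type 2 / 5 / 11, N = 95 | 3.8% | 77.6% |

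The adjusted boundaries are illustrations; the plan specifies none.

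**The case against.** The arithmetic at 85 is not in dispute; the counter-argument is about weight.

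- **The trial may well analyse more than 85.** It enrols 95. Section 8.4.1 analyses all enrolled patients who started treatment with the device, caecal intubation is recorded on day 1 (section 6.1.1), and information is still collected after a post-procedure withdrawal (section 5.4). Patients who withdraw early may be replaced, and for those lost to follow-up section 4.7 says "if the patient is still untraceable it can also be replaced by newly recruited patients". This stands, and it makes the drop-out figures in step 4 pessimistic. It does not remove the problem: replacement is optional, the indicator includes safety to day 7, missing data are not imputed (section 8.5), and the per-protocol set may be smaller.
- **The design is not single-look.** As literally written, with unadjusted looks, power at 85 is 81.3%. That comes with 7.6% type I error, so it is not 80% power at a 5% level. The missing interim adjustment is a separate and more serious matter, and it is sensible to settle both together.
- **The gap is small relative to the uncertainty in the assumption.** Section 8.2 only expects non-completion around 10%. Exact power at 85 reaches 80% at a true rate of 9.7% and falls to 66.9% at 11%. This is fair, but the plan ties its claim to 10.1%.
- **The adjusted-boundary figures depend on the boundary chosen.** Limits of 2 / 4 / 12 at 38 / 57 / 95, for example, give 4.99% type I error and 84.6% power. This also stands; those figures support no more than the statement that 80% at 85 is not restored by the two illustrative boundaries tried there.

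**Conclusion.** The concern holds. Under the plan's own test, level, null rate and assumed rate, power with 85 evaluable patients at a single look is 76.3%, not 80%, because discreteness reduces the actual size to 3.3%. This conclusion rests only on figures printed in the plan and does not depend on which formula produced the 80%. The practical effect is modest. With all 95 analysed, single-look power is 84.0%; at 88–90 it is also above 80%, and at 91–93 it is 77–79%. The 8.4.2 power statements for 38 and 57 patients are correct under the exact test. The final power of the trial remains open until the interim boundary is fixed.

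**What to change.** In section 8.2 and in the synopsis, replace the power statement with one that matches the planned test, for example:

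*For the one-sided exact binomial test at a single look (10.1% against 20%, 5% level), power is about 76% with 85 evaluable patients (reject at 10 or fewer events, size 3.3%) and about 84% if all 95 are evaluable (reject at 12 or fewer events, size 4.2%). These figures will be updated once an alpha-controlling boundary is set for the looks at 38 and 57 patients.*

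The event limits can be carried into the detailed statistical analysis plan, which section 8.4 says will be finalised before database lock. The cost is a text correction in two places and a slightly less favourable stated power at 85. Enrolment, endpoint and choice of test are unchanged.
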